### **5.6.2      *Relatlimab Clinical Pharmacology Summary***

The PK of relatlimab was characterized over a wide range of doses; 20 mg to 800 mg Q2W when administered as monotherapy or 20 mg to 240 mg Q2W and 160 mg to 1440 mg Q4W when administered in combination with nivolumab.

Relatlimab exhibits non-linear and time-varying PK. Nonlinearity in relatlimab CL represents ~31% of total CL of relatlimab at the relatlimab 160-mg dose Q4W in combination with nivolumab. Relatlimab clearance coefficient of variation% (CV%) is 9.7% lower (geometric mean, 5.48 mL/h [41.3%]) at steady state than after the first dose (6.06 mL/h [38.9%])

[REDACTED] The geometric mean value (CV%) for relatlimab volume of distribution at steady state is 6.65 L (19.8%), consistent with the expected distribution of monoclonal antibodies (mAbs) limited to the vascular space. Relatlimab baseline CL in participants receiving relatlimab monotherapy and nivolumab + relatlimab single-agent vial (SAV) (sequential or coadministered) was similar to participants receiving nivolumab + relatlimab FDC ( $\leq 5\%$  and  $\leq 18\%$  difference, respectively), [REDACTED]

## 6 STUDY POPULATION

Prospective approval of protocol deviations to recruitment and enrollment criteria, also known as protocol waivers or exemptions, is not permitted.

### 6.1 Inclusion Criteria

Participants are eligible to be included in the study only if all of the following criteria apply:

#### 1) Signed Written Informed Consent

- a) Participants or their legally acceptable representative (LAR; see [Appendix 2](#)) must have signed and dated an Institutional Review Board (IRB)/Independent Ethics Committee (IEC)-approved written informed consent form (ICF) in accordance with regulatory, local, and institutional guidelines. This must be obtained before the performance of any protocol-related procedures that are not part of normal patient care.
- b) Participants must be willing and able to comply with scheduled visits, treatment schedule, laboratory tests, tumor biopsies, and other requirements of the study.
- c) Participant Re-enrollment: This study permits the re-enrollment of a participant that has discontinued the study as a pre-treatment failure (ie, participant has not been randomized/has not been treated). If re-enrolled, the participant must be re-consented.

#### 2) Type of Participant and Target Disease Characteristics

- a) All participants must have been diagnosed with either Stage IIIA ( $> 1$  mm tumor in lymph node)/B/C/D or Stage IV melanoma by AJCC v8 and have histologically confirmed melanoma that is completely surgically resected (free of disease) with negative margins in order to be eligible. All melanomas, except ocular melanoma, regardless of primary site of disease, will be allowed.

Note: Conjunctival melanoma is not considered to be ocular melanoma and is to be classified as mucosal melanoma.

- b) Participants are eligible if central nervous system (CNS) metastases have been resected and participants are neurologically stable.
  - i) Prior resected CNS metastases must be without evidence of recurrence, as determined by magnetic resonance imaging (MRI) performed at least 4 weeks after resection is complete and within 35 days prior to randomization.
  - ii) Participants must be off immunosuppressive doses of systemic steroids (>10 mg/day prednisone or equivalent) for at least 14 days prior to study drug administration and must have returned to neurologic baseline post-operatively.
  - iii) For CNS lesion(s), a pathology report indicating that there has been complete resection of CNS lesion(s) will suffice as confirmation of negative margins.
- c) Complete resection must be performed [REDACTED] prior to randomization. Management of residual lymph nodes after positive sentinel lymph node biopsy (SLNB) (ie, completion lymph node dissection) will be as per local standards and recommendations for the individual participant.
- d) All participants must have disease-free status documented by a complete physical examination within 14 days prior to randomization and imaging studies within 35 days prior to randomization. Imaging studies must include CT scan of the chest, abdomen, pelvis, and all known sites of resected disease, and brain MRI. See [Section 9.1.2](#) for details and exceptions.

e)

- f) Participants  $\geq$  18 years of age must have an ECOG performance status of  $\leq 1$ . Adolescent participants between 12 and  $< 18$  years of age must have a Lansky/Karnofsky performance score  $\geq 80\%$  ([Appendix 6](#)).
- g) Not applicable - China only.

### 3) Age of Participant

- a) Not applicable per Protocol Amendment 01.
- b) Participant must be  $\geq 12$  years of age or local age of majority inclusive, at the time of signing the informed consent.

**Except:** Where local regulations do not allow for participants  $< 18$  years of age (adolescent population) to participate. For those sites, the eligible participant population is  $\geq 18$  years of age. Refer to [Appendix 9](#).

#### 4) Reproductive Status

Investigators shall counsel women of child bearing potential (WOCBP) on the importance of pregnancy prevention, the implications of an unexpected pregnancy, and the potential of fetal toxicity occurring due to transmission of study intervention to a developing fetus.

The investigator shall evaluate the effectiveness of the contraceptive method in relationship to the first dose of study intervention.

Local laws and regulations may require the use of alternative and/or additional contraception methods.

##### a) Female Participants:

- i) Female participants must have documented proof that they are not of childbearing potential.
- ii) Women who are not of childbearing potential are exempt from contraceptive requirements.
- iii) WOCBP must have a negative highly sensitive negative serum or urine pregnancy test (minimum sensitivity 25 IU/L or equivalent units of HCG) within 24 hours prior to the start of study intervention. An extension up to 72 hours prior to the start of study treatment is permissible in situations where results cannot be obtained within the standard 24-hour window.
  - (1) If a urine test cannot be confirmed as negative (eg, an ambiguous result), a serum pregnancy test is required. In such cases, the participant must be excluded from participation if the serum pregnancy result is positive.
- iv) Additional requirements for pregnancy testing during and after study intervention are located in [Section 2](#), Schedule of Activities.
- v) The investigator is responsible for review of medical history, menstrual history, and recent sexual activity to decrease the risk for inclusion of a woman with an early undetected pregnancy.
- vi) WOCBP must agree to follow instructions for method(s) of contraception defined in [Appendix 4](#) and as described below and included in the ICF.
- vii) WOCBP are permitted to use hormonal contraception methods (as described in [Appendix 4](#)).
- viii) A female participant is eligible to participate if she is not pregnant or breastfeeding, and at least 1 of the following conditions applies:
  - (1) Is not a WOCBP
  - OR
  - (2) Is a WOCBP and using a contraceptive method that is highly effective as described in [Appendix 4](#) during screening and for the duration of treatment for a total of 5 months after the last dose and agrees not to donate eggs (ova, oocytes) for the purpose of reproduction for the same time period.

##### b) Male Participants:

- i) No additional contraceptive measures are required to be used.

## 6.2 Exclusion Criteria

Participants are excluded from the study if any of the following criteria apply:

### 1) Medical Conditions

- a) History of ocular melanoma.

Note: Conjunctival melanoma is not considered to be ocular melanoma and is to be classified as mucosal melanoma.

- b) Untreated/unresected CNS metastases or leptomeningeal metastases.
- c) Participants with an active, known or suspected autoimmune disease. Participants with type I diabetes mellitus, hypothyroidism only requiring hormone replacement, skin disorders (such as vitiligo, psoriasis, or alopecia) not requiring systemic treatment, or conditions not expected to recur in the absence of an external trigger are permitted to enroll.
- d) Participants with serious or uncontrolled medical disorder.
- e) Previous severe acute respiratory syndrome coronavirus 2 (SARS-CoV-2) infection either suspected or confirmed within 4 weeks prior to screening. Acute symptoms must have resolved and based on investigator assessment, there are no sequelae that would place the participant at a higher risk of receiving investigational treatment.

f) [REDACTED]

- g) Participants with a condition requiring systemic treatment with either corticosteroids (> 10 mg daily prednisone equivalent) [REDACTED] or other immunosuppressive medications within 30 days of start of study treatment. Inhaled or topical steroids, and adrenal replacement steroid doses > 10 mg daily prednisone equivalent, are permitted in the absence of active autoimmune disease.
- h) Woman who are breastfeeding.
- i) Participants with a history of myocarditis, regardless of etiology.

### 2) Prior/Concomitant Therapy

[REDACTED]

[REDACTED]

[REDACTED]

[REDACTED]

[REDACTED]

- d) Treatment with complementary medications (eg, herbal supplements or traditional Chinese medicines) to treat the disease under study within 2 weeks prior to randomization. Such medications are permitted if they are used as supportive care. [REDACTED]
- e) Treatment with any live/attenuated vaccine within 30 days of first study treatment (inactivated vaccines are permitted).
- f) Participants currently in other interventional trials, including those for COVID-19, until the protocol specific washout period is achieved. If a study participant has received an investigational COVID-19 vaccine or other investigational product designed to treat or prevent COVID-19 prior to screening, enrollment must be delayed until the full dosing schedule of the vaccine has been completed and the biologic impact of the vaccine or investigational product is stabilized, unless the delay would compromise the participant's health or suitability for enrollment as determined by discussion between the investigator and the Medical Monitor/designee.  
[REDACTED]  
[REDACTED]  
[REDACTED]

### 3) Physical and Laboratory Test Findings

- a) Positive pregnancy test at enrollment or prior to administration of study medication.  
Note: May not transfuse, use growth factors, and/or coagulation factors within 14 days of randomization to meet criteria 3b to 3e.  
[REDACTED]  
[REDACTED]  
[REDACTED]  
[REDACTED]  
[REDACTED]  
[REDACTED]  
[REDACTED]  
[REDACTED]

- k) Known human immunodeficiency virus (HIV) positive with an AIDS defining opportunistic infection within the last year, or a current CD4 count < 350 cells/uL. Participants with HIV are eligible if:
  - i) they have received antiretroviral therapy (ART dosing) for at least 4 weeks prior to randomizations as clinically indicated while enrolled on study
  - ii) they continue on ART as clinically indicated while enrolled on study

iii) CD4 counts and viral load are monitored per standard of care by a local health care provider.

NOTE: Testing for HIV must be performed at sites where mandated locally. HIV positive participants must be excluded where mandated locally (see [Appendix 9](#)).

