**Table 2-1: Screening Procedural Outline (CA224098)**

Procedure	Screening	Notes: a All windows are based on calendar days.
Review of Pathology Report	X	Diagnosis must be stated in a pathology report confirming negative margins that has been finalized prior to randomization. A deidentified copy of the report must be provided to the central lab.
Body Imaging	X	Contrast-enhanced CT of the chest, abdomen, pelvis, and all suspected sites of disease, within 35 days prior to randomization. See Section 9.1.2 for further details and exceptions. Please refer to Appendix 9 for Germany-specific imaging language.
Brain Imaging	X	MRI of the brain (with and without contrast) is required for ALL participants during screening to rule out brain metastases, within 35 days prior to randomization. CT of the brain (with and without contrast) can be performed if MRI is contraindicated. See Section 9.1.2 for further details.
Ultrasound of Region(s) relevant to the Participant's Tumor Resection	X	Ultrasound of region(s) relevant to the participant's tumor resection must be performed for surveillance of participants who have a positive SNLB who do not undergo immediate CLND. Ultrasound is optional for participants who have undergone CLND relevant to the tumor resection. All suspicious lesion(s) should undergo proper evaluation. If disease is detected, all lesions must be removed and NED must be confirmed within 35 days prior to randomization. Ultrasounds should not be submitted to the imaging vendor.
Safety Assessments		
Complete Physical Examination, Measurements, Vital signs	X	Complete physical exam including height, weight, blood pressure, heart rate, and temperature. Must be collected within 14 days prior to randomization.
Performance Status	X	Within 14 days prior to randomization. ECOG Performance Status ( $\geq$ 18 years old) OR Lansky/Karnofsky Performance Score for adolescents (12 to $<$ 18 years old) ( Appendix 6 ).
Assessment of Signs and Symptoms	X	Within 14 days prior to randomization.
Concomitant Medications	X	Within 14 days prior to randomization. Confirm no live vaccine use within 30 days prior to first study treatment.

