**Table 2-1: Screening Procedural Outline (CA224098)**

Procedure	Screening	Notes: a All windows are based on calendar days.
SAE Assessment	X	SAEs collected from time of consent. All AEs (SAEs or non-serious AEs) associated with SARS-CoV-2 infection collected from time of consent.
12-Lead ECG	X	12-lead ECGs should be recorded after the participant has been supine for at least 5 minutes. Must be performed within 14 days prior to randomization. ECG abnormalities should be reviewed and addressed, if needed, prior to randomization.
Laboratory Tests		
Clinical Laboratory Assessments	X	Laboratory tests must be performed within 14 days prior to randomization. Viral testing to be completed within 35 days prior to randomization. For HIV: testing at sites where locally mandated (see Appendix 9 ). Refer to Section 9.4.4 for list of laboratory tests to conduct.
Pregnancy Test (WOCBP)	X	Serum or urine pregnancy test (minimum sensitivity equivalent units 25 IU/L or equivalent units of HCG) to be done within 35 days prior to randomization.
FSH	X	Females under the age of 55 years must have a serum FSH level > 40 mIU/mL to confirm menopause. If not confirmed, protocol pregnancy testing requirements must be followed.

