**Table 2-2: On Study Treatment Procedural Outline (CA224098)**

Procedure	C1D1 a (Cycle Duration = 4 weeks)	C2D1 and D1 of Each Subsequent Cycle ( $\pm$ 3 days)	Notes: b
Study Treatment			
Randomize	X		
IRT Drug Assignment	X		Participant must receive the first dose of study medication within 3 days from randomization.
Dispense Study Treatment	X	X	First drug to be administered within 3 calendar days following randomization, subsequent doses can be administered within 3 days before or after scheduled date if necessary (every 28 days $\pm$ 3 days). Treatment will continue until recurrence, unacceptable toxicity, withdrawal of consent, or after a maximum duration of 1 year from first-dose (maximum of 13 doses), whichever occurs first. See treatment details in Section 7.1.1 .
Safety Assessment			
Targeted Physical Examination, Measurements, and Vital Signs c	X*	X	Weight, blood pressure, heart rate, and temperature within 3 days prior to dosing. *Targeted physical exam not required on C1D1 if a full physical exam was completed within 3 days of first dose.
Performance Status c	X	X	ECOG Performance Status ( $\geq$ 18 years old) OR Lansky/Karnofsky Performance Score for adolescents (12 to $<$ 18 years old). See Appendix 6 .
AE and SAE Assessment	Continuously		Record at each visit. All AEs (SAEs or non-serious AEs), including those associated with SARS-CoV-2 infection, must be collected continuously during the treatment period.
Concomitant Medications	Continuously		Record at each visit.

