**Table 2-2: On Study Treatment Procedural Outline (CA224098)**

Procedure	C1D1 a (Cycle Duration = 4 weeks)	C2D1 and D1 of Each Subsequent Cycle ( $\pm$ 3 days)	Notes: b
Laboratory Tests			
Pregnancy Test (WOCBP)	X*	X ^	
Serum or urine (minimum sensitivity equivalent units 25 IU/L or equivalent units of HCG); a negative pregnancy test should be documented within 1 day prior to administration of first dose of study treatment.
 
[REDACTED]
 
*Pregnancy test not required to be repeated on C1D1 if completed within 24 hours of first dose (during screening).
 
^For subsequent cycles, a negative pregnancy test should be documented within 3 days prior to dosing.

Clinical Laboratory Assessments c	X	X	
Laboratory testing should be performed within 3 days prior to each dose.
 
For the first treatment visit, labs need not be repeated if they were performed within 3 days and the results are available and have been reviewed for eligibility.
 
Refer to Section 9.4.4 for the list of laboratory tests to be conducted.
 
[REDACTED]

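### The 14-day bar on transfusion and growth-factor support runs back from randomization, not from the qualifying blood sample, so a value taken one day after support can satisfy criteria 3b to 3e

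*Combined protocol and SAP*

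**What the plan says.** **Support and laboratory windows.** The note under Section 6.2, Physical and Laboratory Test Findings, reads: "May not transfuse, use growth factors, and/or coagulation factors within 14 days of randomization to meet criteria 3b to 3e". The Clinical Laboratory Assessments row of Table 2-1 says: "Laboratory tests must be performed within 14 days prior to randomization". Section 6.4.1 makes the latest result before randomization the one that decides inclusion, but does not require a late draw. Table 2-2 asks for laboratory tests within 3 days before each dose. It also states: "Participant must receive the first dose of study medication within 3 days from randomization".

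**Order of events.** Table 2-1 (Inclusion/Exclusion Criteria row) and Section 9 require every eligibility criterion to be confirmed before randomization. Section 6 permits no waivers.

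**Pregnancy test.** Section 6.1, item 4(a)(iii), requires a negative test within 24 hours before the start of treatment and adds: "An extension up to 72 hours prior to the start of study treatment is permissible", for cases where the result cannot be had in time. Table 2-2 says "a negative pregnancy test should be documented within 1 day prior to administration of first dose of study treatment" and waives the repeat only for a screening test within 24 hours of first dose. Part of that row is redacted. The screening test in Table 2-1 is "to be done within 35 days prior to randomization".

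**The concern.** A support-free period before a laboratory criterion exists so that the qualifying value reflects the participant's own condition and not recent treatment. It does that only if the period ends at the sample. Here it ends at randomization, which can be up to 14 days after the sample. A site can follow every written rule and still admit someone on a supported value.

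Such a participant is not a protocol deviation, so monitoring would not flag the case. Section 10.3 analyses recurrence-free and overall survival in all randomized participants, so the participant also stays in the primary analysis. The main stake is whether 3b to 3e do the job they were written for.

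The pregnancy-test texts raise a smaller problem of the same family. The criterion is timed to first dose, yet it has to be confirmed before randomization, and the two visible statements of its window differ.

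**Working it through.** The plan states no figure to reproduce on this point; the check is a day count. Set randomization at day 0.

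**Inputs**
- Latest permitted support: T = -15, because days -14 to 0 are barred (Section 6.2 note).
- Qualifying sample: L from -14 to 0 (Table 2-1).
- First dose: F from 0 to 3 (Table 2-2).
- Pre-dose laboratory draw: days F - 3 to F (Table 2-2).

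**Step 1. Days from latest permitted support to the sample:** L - T = L + 15.

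| Sample day L | L + 15 |
|---|---|
| -14 | 1 |
| -7 | 8 |
| 0 | 15 |

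Only a sample on day 0 has the full 14 days clear before it.

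**Step 2. Can the pre-dose draw rescue the criterion?** The same table shows the earliest day on which a pregnancy test can fall under each window in Section 6.1.

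| First dose F | Pre-dose laboratory window | Days in it after randomization | Earliest 24-hour pregnancy test (F - 1) | Earliest 72-hour test (F - 3) |
|---|---|---|---|---|
| 0 | -3 to 0 | none | -1 | -3 |
| 1 | -2 to 1 | 1 | 0 | -2 |
| 2 | -1 to 2 | 1, 2 | 1 | -1 |
| 3 | 0 to 3 | 1, 2, 3 | 2 | 0 |

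If the pre-dose draw is made before randomization, it becomes the deciding value under Section 6.4.1. The interval from day -15 support is then at least 12 days (-3 + 15). With dosing on days 1 to 3 the draw may come after randomization, and the sample from day -14 can be the one that decided eligibility.

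**Step 3. After re-anchoring.** Barring support in the 14 days before the sample gives L - T of at least 15 for every L. For a sample on day -14, the latest permitted support moves from day -15 to day -29 (-14 - 15).

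**Step 4. Pregnancy test.** With dosing on day 2 or 3, a test inside the 24-hour window can only fall after randomization (day 1 or 2 at the earliest). The standard criterion then cannot be confirmed in the order Section 9 requires. The 72-hour extension would allow a test on or before day 0 for every F, but the visible text of Table 2-2 does not carry it.

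**Step 5. Effect on the primary analysis (illustration only).** The documents give neither the number affected nor a visible design hazard ratio. Assume 0.5% to 2% of the planned 1,050 are affected: 0.005 × 1,050 = 5.25 and 0.02 × 1,050 = 21, so about 5 to 21 participants. Assume also a true hazard ratio of 0.80 and, as an extreme, no treatment effect at all in those participants. At 2%, a simple weighted average is 0.98 × 0.80 + 0.02 × 1.00 = 0.804.

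**The case against.** **The two 14-day windows agree.** They do, in length and anchor, so a reader who infers that Section 6.2 and Table 2-1 conflict would be mistaken. The weakness is that neither window ties the bar to the sample, and their agreement is what allows a draw the day after support.

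**The sequence is unlikely, and later checks exist.** It needs support just outside the bar, an early draw and no later result before randomization. Laboratory tests are also due before the first dose, so an old value does not go unchecked before treatment. Both points stand as limits on frequency and exposure. They do not restore the eligibility criterion, because the later draw may follow randomization.

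**The criteria are redacted.** That blood counts or similar values are meant is an inference from the named supports. The anchoring argument does not depend on which values they are.

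**Pregnancy test.** A reader might infer that a 35-day-old test is enough to start treatment. It is not: Table 2-2 requires a test close to the first dose, and exclusion 3(a) itself foresees a check before administration. That a woman may be randomized and then found ineligible is a matter of ordering, not of exposure. The redacted part of the Table 2-2 row may also carry the extension, so only the visible texts can be said to differ.

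**Immunosuppressants.** Exclusion 1(g) covers corticosteroids "or other immunosuppressive medications within 30 days of start of study treatment", while the Concomitant Medications row of Table 2-1 says: "Within 14 days prior to randomization. Confirm no live vaccine use within 30 days prior to first study treatment". A reader might infer that 13 to 16 of the 30 days go unchecked (30 - 17 and 30 - 14, with dosing 0 to 3 days after randomization). The documents do not support this. Neighbouring rows use the same 14-day phrase to say when an assessment is done, and the Inclusion/Exclusion row requires every criterion, 1(g) included, to be confirmed before randomization. Parts of 1(g) and of the Medical History row are also redacted. At most the row's wording could be made clearer.

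**Conclusion.** The point holds for the support-free period. As written, the qualifying sample can follow permitted support by as little as 1 day, and the interval is set by the day of the draw and not by the rule. This rests on reading the note literally and on the inference that 3b to 3e contain values that support would change.

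The consequence is for eligibility integrity and safety. A reader might infer a bias in the recurrence-free survival comparison, but the documents give no basis for a material one: even the extreme illustration moves an assumed hazard ratio of 0.80 only to about 0.804. Keeping randomized but untreated participants in the analysis is ordinary intention-to-treat practice and is not a fault.

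The pregnancy-test point is secondary. The visible windows differ (24 hours extendable to 72 hours, against 1 day), and a criterion timed to first dose cannot always be confirmed before randomization.

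**What to change.** - **Section 6.2 note:** count the existing 14 days back from the blood sample used to meet 3b to 3e instead of from randomization. The length of the period is unchanged.
- **Pregnancy test:** the sponsor should reconcile Section 6.1 item 4(a)(iii), the pregnancy rows of Tables 2-1 and 2-2, and the Section 9 rule on confirming eligibility before randomization. Which window should apply is a clinical decision for the sponsor.
- **Optional wording:** state in the Table 2-1 medication row whether its 14 days give the timing of the review or a look-back.

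The cost is amendment wording, a repeat draw for some participants who recently had support, and perhaps a few more screen failures. The sample size and the analysis do not change.
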